4.1 Design

[figure not shown]
4.1.1 Design Overview

We will use a three-arm, multi-site randomized controlled superiority trial with stratification by SES and parallel design (Aims 1 and 2). One thousand one hundred patients (half higher SES and half lower SES) will be recruited from four large cancer centers over a 18-month period. Randomization will be at the clinician level, nested within study sites, and will involve data analyst blinding. In preparation for the trial, we will conduct semi-structured interviews in Year 1 with women of lower SES who have completed treatment for early stage breast cancer to adapt the “What Matters Most to You” subscale of the Decision Quality Instrument (DQI) for women of lower SES. For Aim 3, we will use interviews, field-notes, and observations to explore strategies that promote the encounter decision aids’ sustained use and dissemination using a theoretical implementation model. See study Gantt Chart on page 46.

4.1.2 Randomized Controlled Superiority Trial (Aims 1 and 2)

According to Cooper et al., the most appropriate design for evaluating interventions that aim to eliminate disparities is a classic experimental design with random assignment to experimental and control groups, with measurements of key variables pre- and post-interventions⁸². We have thus chosen to conduct a three-arm, multi-site randomized controlled superiority trial with stratification by SES (high versus low) and randomization at the clinician level (nested within study sites) (see Fig. 5).

Fig. 5. CONSORT* Study Flow Diagram

*CONSORT stands for Consolidated Standards of Reporting Trials, as reported in the CONSORT statement⁸⁷.

At each site, we will use a cross-sectional study design and randomize participating clinicians (three to five clinicians per site) to one of three arms (Picture Option Grid, Option Grid, or usual

care). We will use an R script written by the study statistician to complete the surgeon randomization. At each site, patients who have given informed consent and are seeing one of the participating clinicians will be allocated to the clinician's corresponding arm (Picture Option Grid, Option Grid, or usual care). Approximately the same number of patients in each socioeconomic stratum will be allocated to each arm. We will monitor accrual within each arm for each socioeconomic stratum at each site to ensure that a similar number of patients in each socioeconomic stratum receive each treatment. The total number of patients recruited at each site will be allowed to vary.

4.1.3 Controlling for Contamination

Since the randomization occurs at the clinician level, we are confident that the risk of contamination will be minimal⁸⁸. However, to control for any potential contamination and assess the fidelity of delivering each intervention, we will audio-record a sample of clinical encounters. We will record consented patients. The digital recorder will be constantly present in the consulting room and a research assistant will be present to turn the recorder on when required. The research assistant will enter the room each time so the breast surgeon does not know when they are being recorded. The recording light on each recorder will be taped over so recording status can not be discerned. We will also ask all patients to indicate at T2 which intervention was used in the encounter, using images of each intervention, and will use both intention-to-treat and as-treated analyses. We will train all clinicians in delivering the intervention according to their allocated arm. Clinicians in usual care will not be trained in the use of the interventions. If there is residual contamination, the bias will be towards a null effect. We will therefore be confident that any significant findings are actual and arise as a result of the interventions. Since there are many more physicians than centers, we anticipate having greater power with physician level randomization than with site level randomization, even if the effect size we estimate is reduced by contamination.

4.1.4 Adapting the Decision Quality Instrument

In preparation for the comparative effectiveness trial, we will adapt the "What Matters Most to You" subscale of the Decision Quality Instrument (DQI)⁸⁹. We aim to capture the factors (including potential barriers) that are important to women of lower SES when deciding about early stage breast cancer treatments and that are not currently captured in the DQI. We will conduct up to 45 semi-structured interviews with women of lower SES in both urban and rural settings.

4.2 Setting

The DQI adaptation interviews and randomized controlled trial will be conducted at four large cancer centers in the USA. The four study sites include:

- Dartmouth-Hitchcock, Lebanon, NH and Manchester, NH
- New York University (NYU) School of Medicine, New York, NY
- Montefiore Medical Center, Bronx, NY
- Joanne Knight Breast Health Center, St. Louis, MO

4.3 Participants

4.3.1 Randomized Controlled Superiority Trial (Aims 1 and 2)

We will include 600 women at least 18 years of age with a confirmed diagnosis of early stage breast cancer (I to IIIA) (see inclusion/exclusion criteria below). Approximately half will be on

Medicaid or Medicare without supplemental insurance, or uninsured (lower SES population) and about half will be women with private insurance or Medicare with supplemental insurance (higher SES population) (see 4.3.4 for stratification by SES).

Participants will be recruited across the four study sites over 18 months.

To facilitate recruitment and retention, participants will be compensated for their time with a \$15 gift card at T2, T3, T4, and T5.

Participant Inclusion Criteria

The study team at each study site will use the following inclusion criteria:

- Assigned female at birth;
- At least 18 years of age;
- Confirmed diagnosis (via biopsy) of early stage breast cancer (stages I-IIIA);
- Eligible for both breast-conserving surgery and mastectomy based on medical records and clinician's opinion before surgery;
- Spoken English, Spanish, or Mandarin Chinese.

Participant Exclusion Criteria

The following exclusion criteria will be used:

- Transgender men and women;
- Women who have undergone prophylactic mastectomy;
- Women with visual impairment (because of the visual nature of the Picture Option Grid);
- Women with a diagnosis of severe mental illness or severe dementia;
- Women with inflammatory breast carcinoma.

Women who are receiving neoadjuvant therapy will be invited to take part in the study in the first nine months of the trial in order to be able to complete all follow-up assessments before the end of the trial. Their T3 assessment will occur after the neoadjuvant therapy has been completed and post-surgery. This may occur up to 7 months after T0 (baseline).

4.3.2 DQI Adaptation (Year 1)

We will recruit up to 45 women of lower SES who have completed treatments for early stage breast cancer in the past three years to adapt the What Matters Most subscale of the DQI. We will use purposive sampling. Participants will receive a \$15 gift card.

Participant Inclusion Criteria

- Assigned female at birth;
- Between the ages of 18 and 74 years of age;
- Government insured (without supplemental insurance) or uninsured (as well as ACA marketplace plans);

- 138% of the federal poverty level or below;
- Breast cancer surgery and radiation have been completed in the past three years;
- At least spoken English.

Participant Exclusion Criteria

The following exclusion criteria will be used:

- Transgender men and women;
- Women who have undergone prophylactic mastectomy;
- Women >74 years of age (as other treatment options may be relevant);
- Women who are unable to complete the study procedures due to mental health impairment, cognitive impairment, or visual issues, as determined by the research staff or medical chart;
- Women with inflammatory breast carcinoma.

4.3.3 Explore Strategies that Promote the Encounter Decision Aids' Sustained Use and Dissemination (Aim 3)

We will conduct up to 100 interviews in total for Aim 3. A purposive sample of 60 participants balanced in arm, SES, and age will be invited to take part in a semi-structured interview after completion of the final follow-up assessment (T4). We will also encourage the participant's family or caregivers who are supporting the patient in making treatment decisions to attend the interview and share their perspective. Patients will be compensated with a \$30 gift card. We will also include up to 10 healthcare professionals and other stakeholders per site, with and without involvement in the trial (up to 40 in total).

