3.1 Background and Rationale

3.1.1 Impact of the Condition on the Health of Individuals and Populations

Breast cancer is the most commonly diagnosed malignancy and second leading cause of death in women^{3,4}. Despite significant improvements in overall breast cancer survival, disparities persist in breast cancer treatment, communication in healthcare, long-term health outcomes and mortality^{5,6}. Extensive evidence suggests that women of lower socioeconomic status (SES) diagnosed with early stage breast cancer have significantly poorer communication with their clinicians, lower knowledge of breast cancer surgery options, higher uptake of mastectomy, and worse cancer-related and patient-centered health outcomes compared to women of higher SES⁵⁻¹³. They also tend to receive breast cancer care that is inferior to that offered to women of higher SES and that deviates from established clinical guidelines (e.g., inconsistent use of radiation after breast conserving surgery; BCS)^{6,12}. For the purpose of recruiting participants into the study, we define low SES as meeting the following two criteria: 1) 138% of the Federal Poverty Level or below and 2) uninsured or government-insured status (Medicaid or Medicare without supplemental insurance) or Accountable Care Act (ACA) marketplace plans^{14,15}. Although educational attainment will not be used as part of the inclusion criteria, we will examine it using multiple informants analysis (see analysis section) and include it in our overall definition of lower SES. This definition is considered valid and relevant to the populations and outcomes under study^{14,16}.

SES-linked differences in early stage breast cancer care meet the Institute of Medicine (IOM)'s definition of a health service disparity: a difference in treatment or access not justified by differences in health status or preferences of the population groups¹⁷. There is no evidence that women of lower SES have distinct values and preferences that explain a significantly lower uptake of BCS and limited engagement in decision-making^{6,10,11}. Differences in treatment received, doctor-patient communication, engagement in decision-making, and patient-centered health outcomes are disparities that predominantly affect women of low SES with early stage breast cancer, irrespective of race or ethnicity^{5,11,18}. For early stage breast cancer, low SES is a stronger predictor of poor outcomes and treatment received than race or ethnicity^{19,20}.

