Tailoring Information to Reduce Disparities. When preparing information for low SES populations, it is imperative to recognize the barriers of limited health literacy and numeracy and to consider the use of images and easy-to-access formats such as paper-based interventions. Approximately 80 million US adults, many of whom have low SES, have low textual literacy and limited health literacy⁶⁶⁻⁶⁸. Healthcare professionals consider low health literacy a major barrier to involving patients in treatment decisions^{44,69,70}. Patients' abilities to benefit from decision aids largely depend on their capacity to understand and use the interventions available to them^{44,70}. Tailoring information to patients of low SES, who typically have low health literacy, is essential, though it is largely overlooked^{11,45}.

Our proposal seeks to challenge this highly textual literacy-assuming paradigm, by comparing a validated pictorial encounter decision aid (Picture Option Grid) to a validated text-based encounter decision aid (Option Grid) across socioeconomic strata.

Pictorial superiority is defined as the tendency to understand and remember concrete items more

Fig 1. Encounter decision aids (Option Grid left; Picture Option Grid right)

[figure not shown]
[figure not shown]

Fig 2. Pictorial superiority

easily when they are presented as pictures rather than words (see Fig. 2)⁷¹. Pictures facilitate conceptual processing and demand less cognitive effort than words^{72,73}. There is evidence of visual literacy in people of lower textual literacy⁷⁴. Research confirms that the use of pictures promotes understanding, compliance, and recall associated with health education information^{74,75}. No studies have yet to compare the effectiveness of a pictorial encounter decision aid to a text-based encounter decision aid across socioeconomic strata.

Evidence Gap 2: Why are Women of Low SES More Likely to Choose Mastectomy?

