Treatment disparities in breast cancer care have been extensively examined^{5,11,12,18,76-81}. The literature suggests that treatment disparities are associated with patient-, clinician-, and system-level factors^{76,82}. The reasons women of low SES are more likely to choose mastectomy over BCS, however, are not well defined¹⁰. A higher uptake of mastectomy in this group would not be a concern, provided that this choice was the result of an informed preference and not a treatment disparity (i.e., treatment not justified by differences in health status or preferences of the population group). In fact, there is no evidence that women of low SES have clear preferences for mastectomy¹⁰. Based on extensive research evidence^{5,6,9,11,12,18}, we hypothesize that there is indeed a treatment disparity, which is strongly associated with less effective communication, lower knowledge of breast cancer surgery, and less participation in decision-making^{10,11,13}.

Other factors, such as limited financial resources and lack of insurance coverage, do not seem to predict decision-making for early stage breast cancer surgery⁸³. There is no significant difference in monetary cost to patients between BCS and mastectomy, as BCS has higher short-term cost but lower long-term cost⁸⁴. For many women of low SES, Medicare and other programs targeted at lower SES groups would cover the costs of either treatment, thus minimizing the impact of cost on decision-making. Other patient-level factors, such as childcare, transportation expenses, and other financial pressures (e.g., a need to return to work quickly) may be strong influences on the treatment choices of women of low SES irrespective of knowledge and participation in decision-making. The impact of these factors, however, is unclear and has not been demonstrated to date^{85,86}. According to the literature, communication, accessible information, and participation in decision-making seem to play a significant (possibly the most significant) role in decision-making^{5,6,9,11,12,18}. We hypothesize that encounter decision aids can address these issues and reduce disparities across socioeconomic strata. However, since it remains unclear how other factors (limited financial resources and other socioeconomic barriers) may affect decision-making, we will explore, in Aim 2, factors that may be mediating and moderating the intervention's effect^{10,11,13,39}.

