8.1 Adapting the Decision Quality Instrument (DQI) Subscale (Year 1)

8.1.1 Risk to Human Subjects

Human Subjects Involvement, Characteristics, and Design

In preparation for the comparative effectiveness trial, we will adapt the “What Matters Most to You” subscale of the Decision Quality Instrument. We will conduct up to 45 semi-structured interviews with women of lower SES at all four cancer centers involved in the trial. As mentioned in the Research Strategy section, we will include women over 18 years of age of lower SES who are uninsured or on Medicaid or Medicare without supplemental insurance (or ACA marketplace plans) who have completed treatments in the past three years. We will exclude women over 75 years of age and those with visual impairment, a diagnosis of psychosis or severe dementia, or inflammatory breast carcinoma.

Sources of Materials

In conducting the semi-structured interviews, we will collect information on participant characteristics (i.e., age, race, ethnicity, median household income, insurance status, highest educational attainment, and health literacy). The interviews will seek to understand which factors affect women’s treatment decisions related to breast cancer in women of lower SES. We will remove any identifying information from the audio-recording transcripts. We will not require participants to provide written consent to take part in the interviews but will audio-record participants’ verbal consent at the interview’s outset. At the Joanne Knight Breast Health Center, written informed consent will be obtained. Each audio recording will be labeled with a unique, anonymous study identification (SI) number. A record of the names, contact

details of the participants, and their unique SI numbers will be stored securely in the REDCap database and separately from the audio recordings.

Potential Risks

We do not anticipate any physical, financial, legal, or other risks to the interview participants beyond those of natural occurrence. We anticipate potential risks to be limited to psychological discomfort. If this were to occur, we will immediately terminate the interview and ensure that appropriate support (such as access to a psychologist or social worker) is provided. Interviews will be conducted in private.

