11 APPENDIX A. OPTION GRID

Breast cancer: surgical options

Use this **Option Grid™** decision aid to help you and your healthcare professional talk about how to best treat your breast cancer. This decision aid is for women with early stage breast cancer (stages I to IIIA).

Frequently asked questions	Lumpectomy with radiation	Mastectomy
What is removed?	The cancer lump is removed, with some surrounding tissue.	The whole breast is removed.
Which surgery is best for long-term survival?	Long-term survival rates are the same for both surgeries.	Long-term survival rates are the same for both surgeries.
What are the chances of cancer coming back in the breast?	Breast cancer will come back in the breast in about 5 to 10 in 100 women (5-10%) in the 10 years after a lumpectomy.	Breast cancer will come back in the area of the scar in about 5 to 10 in 100 women (5-10%) in the 10 years after a mastectomy.
Will I need more than one surgery?	Possibly, 20 in 100 women (20%) may need another surgery to remove breast tissue or lymph node that have cancer.	Possibly, if your lymph nodes have cancer. Yes, if you choose breast reconstruction.
How long will it take to recover?	Most women are home within 24 hours of surgery.	Most women are home within 24 hours of surgery. It may take longer with reconstruction.
Will I need radiation after surgery?	Yes, for up to seven weeks after surgery.	Radiation is not usually given after mastectomy.
Will my lymph nodes be removed?	If cancer has spread to the lymph nodes under your arm, your doctor will discuss with you whether you need more treatment such as surgery or radiotherapy.	If cancer has spread to the lymph nodes under your arm, your doctor will discuss with you whether you need more treatment such as surgery or radiotherapy.
Will I need chemotherapy?	You may be offered chemotherapy, but this does not depend on the surgery you choose.	You may be offered chemotherapy, but this does not depend on the surgery you choose.
Will I lose my hair?	Hair loss is common after chemotherapy.	Hair loss is common after chemotherapy.

Editors: [name] (Lead Editor), [name], [name], [name], [name], [name], [name]

Evidence document: <http://optiongrid.org/admin/resources/grid/evidences/9.pdf?x=WBZ1nd4YE>

This Option Grid does not constitute medical advice, diagnosis, or treatment. See Terms of Use and Privacy Policy at www.optiongrid.org.

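### Read literally, the inclusion bullet for the DQI adaptation interviews excludes women who had no radiation, chiefly mastectomy patients, and it conflicts with two other descriptions of the same sample

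*Combined protocol and SAP*

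**What the plan says.** Section 4.1.4 gives the purpose of the Year 1 interviews: "We aim to capture the factors (including potential barriers) that are important to women of lower SES" in choosing treatment and that the DQI does not yet cover.

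Three passages describe who is interviewed:

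- The lead sentence of 4.3.2 asks for up to 45 women of lower SES "who have completed treatments for early stage breast cancer in the past three years". Sampling is purposive, and surgery type is not named as a sampling factor.
- The inclusion list of 4.3.2 asks: "Breast cancer surgery and radiation have been completed in the past three years".
- Section 8.1.1, on the same interviews, asks for women "who have completed treatments in the past three years".

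Two passages bear on who receives radiation. The Option Grid in Appendix A says "Radiation is not usually given after mastectomy"; the Picture Option Grid in Appendix B agrees but adds that it is sometimes recommended. Section 3.1.1 notes "inconsistent use of radiation after breast conserving surgery" as an example of the care that women of lower SES receive.

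Section 3.1.2 makes mastectomy in this population a named evidence gap, under the heading "Why are Women of Low SES More Likely to Choose Mastectomy", and says: "The reasons women of low SES are more likely to choose mastectomy over BCS, however, are not well defined". In section 3.2, Aim 2 Hypothesis 2 treats values from the subscale as mediators of treatment choice. Hypothesis 3 treats socioeconomic barriers reported in the DQI as moderators.

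**The concern.** The bullet joins surgery and radiation with a plain conjunction and has no clause for women who were given no radiation. A site that screens by the bullet would accept a woman after lumpectomy with radiation and turn away a woman after mastectomy alone. It would also turn away a woman who had BCS without radiation.

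The interviews are the plan's means of finding values and barriers that the subscale misses. If women who had a mastectomy without radiation are few or absent, their reasons have less chance of being heard. The bullet also selects on something close to what is being studied, because item 1.3 of the subscale asks about avoiding radiation. Section 3.1.2 names childcare, transport costs and a quick return to work as possible influences on choice, and Appendix B describes radiation as hospital visits on five days of each week for as long as seven weeks. Section 1 of the Appendix C worksheet has no fixed item on work, travel or cost; only the free-text item 1.6 could pick these up.

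At stake is how complete the new values and barriers are for the exploratory analyses under Aim 2, Hypotheses 2 and 3.

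**Working it through.** The plan states no figure on this point, so there is none to reproduce. The check sets the passages side by side and then illustrates a possible size.

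**Step 1. Who qualifies under each wording**

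| Treatment, finished within three years | Bullet in 4.3.2, read literally | Lead sentence of 4.3.2, and 8.1.1 |
|---|---|---|
| BCS with radiation | meets | meets |
| BCS without radiation | fails | meets |
| Mastectomy with radiation | meets | meets |
| Mastectomy without radiation | fails | meets |

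The wordings disagree in two of the four rows. By the Option Grid's own statement, the last row is the usual situation after mastectomy.

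**Step 2. Whether sampling can repair it**

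Purposive sampling can favour some eligible women over others. It can raise the number who had a mastectomy with radiation, but it cannot recruit women whom the inclusion list makes ineligible.

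**Step 3. Illustrative size**

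The documents give none of the rates needed, so all three are assumptions:

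- m, the share of otherwise suitable women who had a mastectomy: 30% to 60%
- r, the share given radiation after mastectomy: 10% to 40%
- b, the share given radiation after BCS: 80% to 100%

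Share of mastectomy patients excluded = 1 − r, which is 60% to 90%.

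Mastectomy share of the women left eligible = m·r / (m·r + (1 − m)·b):

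- Low end (m = 0.3, r = 0.1, b = 1.0): 0.03 / (0.03 + 0.70) = 4.1%. Times 45 = 1.8 women, against 0.3 × 45 = 13.5 without the radiation condition.
- Middle (m = 0.5, r = 0.2, b = 1.0): 0.10 / (0.10 + 0.50) = 16.7%. Times 45 = 7.5, against 22.5.
- High end (m = 0.6, r = 0.4, b = 0.8): 0.24 / (0.24 + 0.32) = 42.9%. Times 45 = 19.3, against 27.

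These counts assume that interviewees are drawn in proportion to the eligible pool. The two ranges (about 2 to 19, and 13.5 to 27) overlap, so no single reduction can be claimed. The direction is firmer: for any given m, the share falls below m whenever r is smaller than b.

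**Step 4. Whether the excluded are chiefly mastectomy patients**

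Excluded mastectomy patients are m(1 − r) of the pool, and excluded BCS patients are (1 − m)(1 − b). The corner of the assumed ranges least favourable to the word chiefly is m = 0.3, r = 0.4, b = 0.8. It gives 0.18 against 0.14, so mastectomy patients are 0.18 / 0.32 = 56% of the excluded. At m = 0.5, r = 0.2, b = 0.8 it is 0.40 against 0.10, or 80%.

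**Step 5. How far it reaches**

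Trial eligibility (4.3.1) has no radiation condition. The power calculation (4.8.1) and the Aim 1 analysis (4.8.3) do not use the interview sample. Items 1.1 to 1.5 do not depend on who is interviewed about missing factors. What remains exposed is the search for additional values and barriers, and through it the exploratory Aim 2 analyses.

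**The case against.** The strongest reply is that the bullet means surgery, and any radiation given, have finished. The lead sentence of the same section and 8.1.1 both speak only of completed treatment, and nothing in the documents shows that a site applied the literal reading. This stands as far as it goes: the exclusion is conditional on that reading. It does not remove the conflict. The inclusion list is what a screener applies, and it is narrower than both descriptions. Section 8.1.1 is not a safe gloss on it either: it omits the income criterion and words the upper age exclusion differently (over 75, against over 74 in 4.3.2).

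A reader might infer that the concordance score and the mediation analysis would rest on values from one side of the choice. The documents do not support that. The interviews adapt an existing validated instrument, and its items already cover the mastectomy side: 1.2 on removing the breast for peace of mind, 1.3 on avoiding radiation and 1.4 on reconstruction. Hypothesis 2 itself names removal for peace of mind and avoidance of radiation among the mediating values.

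A reader might also take mastectomy patients to be the group that the adaptation is for. Section 4.1.4 names women of lower SES generally, and pressures such as work and travel can be reported by women who had a lumpectomy. Mastectomy patients are a key group because of Evidence Gap 2, but not the only one.

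Finally, a remedy may come late. Table 5 sets the adaptation for completion by 6/30/17. The current text cuts the sample to 600 because of recruitment difficulties, so it was probably written after enrolment began. This is a fair point about which part of the fix applies.

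**Conclusion.** The point holds as a conflict between passages with a plausible effect on the interview sample. As written, the inclusion bullet excludes women who had no radiation: chiefly those who had a mastectomy, and also those who had BCS alone. The two other descriptions admit them. A key group for Evidence Gap 2 could therefore be under-represented when new values and barriers are sought for the subscale.

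The documents do not show that such women were in fact turned away, and they do not allow the loss to be sized. The illustrative counts rest on three assumed rates and a proportional draw, which purposive sampling need not follow. The consequence is confined to the values and barriers used in exploratory analyses under Aim 2, Hypotheses 2 and 3. It is a modest defect that is worth correcting because correction is cheap.

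**What to change.** Reconcile the bullet in 4.3.2 with its lead sentence and with 8.1.1. Reword it to require that surgery was completed in the past three years, and that radiation was completed where it was given. This admits both excluded groups. Make surgery type (mastectomy or BCS) a purposive-sampling factor within the existing limit of 45. The cost is one clause and one sampling instruction, with no added interviews.

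If the interviews are finished, report the interviewees by surgery type and by whether radiation was given. If few had a mastectomy without radiation, state this as a limit on the Aim 2 analyses of values and barriers, and review the free-text responses to item 1.6 that the trial already collects. That review is a small extra piece of qualitative coding and needs no new data collection.
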